#### Syntax:

```
proc mi data=datain out=dataout seed=&seed. Nimpute=25 <options>; where trtpn=(TRT); /* Note TRT = [1, 2]; depending on treatment group */; mcmc chain=single; var baseline week1 week2 week3 week4 week5 week6 week7 week8 week9 week10; run;
```

3. From each complete dataset, the dichotomous responder rate will be determined. Each complete dataset will be analyzed as specified for the particular analysis.

The results from the analyses will be combined into a single inference using SAS® PROC MIANALYZE. In the case of the primary analysis and the secondary responder analyses, the Cochran Mantel Haenszel (CMH) statistics computed in the analyses of WI-NRS responder rates will be normalized using the Wilson-Hilferty transformation prior to combining them using SAS® PROC MIANALYZE.

A total of 2 random seeds will be needed to impute missing data. Those random seeds have been pre-specified by using a random number generator:

• WI-NRS Serlopitant: Seed= 1537248074

• WI-NRS Placebo: Seed= 474752918

### 6.1.6 Interim Analyses and Data Monitoring

No interim analyses will be performed.

#### **6.1.7** Multicenter Studies

The clinical study will be conducted under a common protocol for each investigational site with the intention of pooling all data for analysis. Every effort will be made to promote consistency in study execution at each study site.

### 6.1.8 Multiple Comparisons/Multiplicity

The primary and key secondary endpoints will be analyzed. However, the statistical significance of the key secondary endpoints will only be considered should statistical significance be reached for the primary endpoint. Similarly, statistical significance within the key secondary endpoints will be considered based on a hierarchical approach, starting with the WI-NRS Week 4 responder rate followed by the WI-NRS Week 2 responder rate. If the first key secondary

endpoint fails to reach statistical significance at a level of 0.05, then subsequent endpoints will not be considered statistically significant.

### **6.1.9** Examination of Subgroups

Descriptive summaries of the primary efficacy endpoint will be created for subgroups of the Intent-to-Treat (ITT) population. Subgroups include age (< median age; >= median age), sex, ethnicity, race and Baseline WI-NRS randomization strata.

### 6.2 Disposition of Subjects

An accounting of all randomized subjects by disposition will be presented. Subjects who discontinue study drug prematurely or withdraw from the study will be summarized and listed, with a description of the reason for early termination/withdrawal.

The number of subjects included in each population will be summarized. Subjects who are excluded from a population will be summarized by the reasons for exclusion.

#### **6.3** Protocol Deviations

Protocol deviations leading to exclusion from an analysis population will be tabulated. Other protocol deviations will be presented in a data listing.

### 6.4 Data Sets Analyzed

The following analysis populations will be reviewed and approved by the Sponsor prior to unblinding the study.

### 6.4.1 Intent-to-Treat (ITT) Population

The primary efficacy population will be the ITT population, which will include all randomized subjects who were dispensed study drug. Subjects will be analyzed within the treatment group to which they are randomized.

#### 6.4.2 Safety Population

The primary safety population will be all treated subjects with at least one post-baseline assessment or a reported TEAE. For safety analyses, subjects will be classified based upon treatment received. In the case that a subject received both treatments, subjects will be summarized within the serlopitant 5 mg group.

### 6.4.3 Per Protocol Population

Additional analyses performed on the Per Protocol (PP) population will be considered supportive. The PP population will include all subjects in the safety population who complete the

Week 10 evaluations without any significant protocol deviations/violations (i.e., any subject or investigator activity that could have possibly interfered with the therapeutic administration of the treatment or the precise evaluation of treatment efficacy). The PP population will include subjects in the safety population who do not meet any of the following criteria:

- Violated the inclusion/exclusion criteria;
- Received a strong CYP3A4 inhibitor (See Appendix B in the Protocol);
- Received an excluded medication which may plausibly impact the primary endpoint at Week 10 (e.g. was provided to treat pruritus or PN);
- Have not been compliant with the dosing regimen (i.e. subjects must comply with 80-120% of the expected dosage of study medication during participation in the study);
- Have not completed Week 10 visit within  $\pm 7$  days window
- Have not completed the eDiary to provide the Week 10 WI-NRS Primary Endpoint

Subjects who discontinue from the study drug due to an adverse event related to study treatment or documented lack of treatment effect, or who met protocol-defined non-responder criteria, will be included in the PP population. Prior to breaking the blind other additional criteria may be added to the lists above to accommodate for unforeseen events that occurred during the conduct of the trial that result in noteworthy study protocol deviations.

Subjects will be analyzed within the treatment group to which they are randomized.

### 6.5 Demographic and Other Baseline Characteristics

Demographic and baseline characteristics summaries will be done for the ITT, Safety, and PP populations.

Sex, race, and ethnicity will be summarized by counts and percentages. Age, height (cm), and weight (kg) will be summarized with descriptive statistics.

IGA PN-A, and IGA PN-S will be summarized by counts and percentages. WI-NRS (average result measured over the week prior to treatment) and DLQI will be summarized with descriptive statistics.

Medical histories will be coded using MedDRA, tabulated by System Organ Class and Preferred Term for the Safety population, and presented in a by-subject listing.

PN history and prior PN therapies will be presented in by-subject listings.

#### 6.6 Prior and Concomitant Medications

Prior and concomitant medications will be coded by the WHO-DDE to Anatomical Therapeutic Classification (ATC) and preferred drug name. Concomitant medications will be summarized by ATC level 2 term and preferred drug name.

A by-subject listing of all prior and concomitant medications will be presented. The associated by-subject listing will have a prior/concomitant determination that is based on the date of first dose.

### 6.7 Analysis of Efficacy

The efficacy endpoints will be summarized within the ITT and PP populations using descriptive statistics by time point and treatment. Available results including averaged imputed values, as well as change from baseline, will be summarized for each applicable time point. The WI-NRS and change from baseline will also be presented for each study day in a by-subject listing.

For the 4- and 3-point responder rate endpoints, subjects will be considered responders if they have at least a 4- / 3-point reduction between baseline and the corresponding week. Subjects that discontinued study drug due to lack of efficacy or used an excluded medication to treat worsening of pruritus or PN will be considered non-responders.

### 6.7.1 Primary Efficacy Analysis

The difference in the primary efficacy outcome measure (WI-NRS 4-point responder rate at Week 10) will be tested using a CMH test controlling for the 'as randomized' stratification factors. Conceptually the hypotheses being tested are:

$$H_0$$
:  $P_{Placebo} \ge P_{Serlopitant}$   $H_a$ :  $P_{Placebo} < P_{Serlopitant}$ 

where  $P_{Placebo}$  is the percent of placebo responders and  $P_{Serlopitant}$  is the similar percent for serlopitant.

### 6.7.2 Key Secondary Efficacy Analysis

The WI-NRS 4-point responder rates at Week 4 and Week 2 will be analyzed using methods consistent with testing the primary endpoint.

The preceding analyses are to be conducted for the ITT and PP populations.

# 6.7.3 Additional Secondary Efficacy Analysis

Additional secondary efficacy endpoints which may be drawn from the primary and key secondary imputations (including all WI-NRS endpoints) will be analyzed using the imputed

data. Additional secondary efficacy endpoints otherwise will be analyzed using available data. P-values will be included for descriptive purposes only.

Additional secondary efficacy endpoints which are dichotomous (responder) will include analyses analogous to the primary and key secondary efficacy analyses.

Additional secondary efficacy endpoints based on change from baseline will be analyzed using an analysis of covariance (ANCOVA) model with treatment group and stratification factor as fixed effects and the baseline value as a covariate. Both least squares means and observed means will be presented.

To confirm the assumptions for the ANCOVA model (i.e., that the errors are normally distributed with equal variances), residuals will be examined using the Shapiro-Wilk test. If there is overwhelmingly strong evidence that the assumptions are not satisfied, the data will be rank-transformed prior to submitting to the ANCOVA. Results of the rank-transformed analysis then will be considered the primary analysis; however, results of the non-rank transformed analysis will also be presented.

### 6.8 Sensitivity Analysis

#### **6.8.1** Last Observation Carried Forward

In the first set of sensitivity analyses, missing values will be imputed using LOCF. Data will be imputed using LOCF unless the subject withdrew from the study due to lack of efficacy, or the subject used an excluded therapy to treat worsening of pruritus or PN, in which case their responder status will be defined as non-responder. Each primary and key secondary endpoint will be analyzed as it was using the multiply imputed data.

#### **6.8.2** Repeated Measures Analysis

The second set of sensitivity analyses will be performed on observed data.

The dichotomized primary and key secondary WI-NRS endpoints will each be analyzed with a repeated measures logistic regression model (generalized estimating equations), with the dichotomized endpoint as the dependent variable and treatment, stratification factor and visit (Weeks 1-10) as independent factors.

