In the first set of sensitivity analysis, missing values will be imputed using LOCF. Data will be imputed using LOCF unless the subject withdrew from the study due to a lack of efficacy, or the subject used an excluded therapy to treat worsening of pruritus or PN, in which case their responder status will be defined as non-responder. Each primary and key secondary endpoint will be analyzed as it was using the multiply imputed data.

8.9.2 *Repeated Measures Analysis*

The second set of sensitivity analyses will be performed on observed data.

The dichotomized primary and key secondary WI-NRS endpoints will be analyzed with a repeated measures logistic regression model (generalized estimating equations), with the dichotomized endpoint as the dependent variable and treatment, stratification factor and visit (Weeks 2, 4, 10) as independent factors

Change from baseline in DLQI to Week 10 will be analyzed with a repeated measures ANCOVA, with treatment, stratification factor and applicable timepoints as independent factors and a covariate of baseline value.

8.9.3 *Tipping Point Analysis*

A sensitivity analysis for the handling of missing data for the primary efficacy endpoint will be carried out using a tipping point analysis.

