#### 8. CHANGES IN THE PLANNED ANALYSES

No changes to planned analyses.

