<sup>a Counts reflect numbers of subjects reporting one or more concomitant medications that map to the WHO-DDE. At each level of summarization (ATC Level 2 Term or Standard Medication Name) subjects are counted once.

Note: WHO Drug Dictionary, Version September 1, 2018.

SOURCE: USERNAME\SPONSOR\PROJECT\JOBNAME (DATE,TIME)

Table 14.2.1.1: Analysis of the Primary Efficacy Endpoint: Worst-Itch Numeric Rating Scale (WI-NRS) 4-Point Responder at Week 10 (Intent-to-Treat Population)

	Placebo (N=xxx)	Serlopitant 5 mg (N=xxx)	P-value a
At Least 4-Point Reduction from Baseline in			
Weekly Average WI-NRS at Week 10			
Success	xx.xx%	XX.XX  / 0	x.xxx
Failure	xx.xx%	XX.XX  / 0	

<sup>a P-value from a Cochran Mantel Haenszel (CMH) test stratified by Baseline WI-NRS used for randomization stratification. Value has been adjusted for multiple imputation.

Note: Multiple imputation (MCMC) used to impute missing values. Summary statistics represent average values, obtained by averaging the summary statistics generated from each imputed dataset.

SOURCE: USERNAME\SPONSOR\PROJECT\JOBNAME (DATE,TIME)

Repeat Table 14.2.1.1 for the following:

Table 14.2.1.2: Analysis of the Primary Efficacy Endpoint: Worst-Itch Numeric Rating Scale (WI-NRS) 4-Point Responder at Week 10 (Per-Protocol Population)

[figure not shown]
Table 14.2.1.3: Sensitivity Analyses of the Primary Efficacy Endpoint: Worst-Itch Numeric Rating Scale (WI-NRS) 4-Point Responder at Week 10 (Intent-to-Treat Population)

	Placebo (N=xxx)	Serlopitant 5 mg (N=xxx)	P-value
Missing Values Imputed using Last Observation Carried Forward (LOCF)	, ,	,	
At Least 4-Point Reduction from Baseline in Weekly Average WI-NRS at Week 10			
Success	xx ( xx.x%)	xx ( xx.x%)	x.xxx a
Failure	xx ( xx.x%)	xx ( xx.x%)	
Repeated Measures Analysis on Observed			
Data			
At Least 4-Point Reduction from Baseline in			
Weekly Average WI-NRS at Week 10			
Success	xx.xx%	XX.XX%	x.xxx b
Failure	xx.xx%	xx.xx%	

<sup>a P-value from a Cochran Mantel Haenszel (CMH) test stratified by Baseline WI-NRS randomization stratification.

<sup>b P-value from a repeated measures logistic regression with factors of treatment group, randomization stratification, visit and treatment group by visit interaction.

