<sup>a P-value from a Cochran Mantel Haenszel (CMH) test stratified by Baseline WI-NRS used for randomization stratification. Value has been adjusted for multiple imputation.

Note: Multiple imputation (MCMC) used to impute missing values. Change calculated as post-baseline – baseline.

SOURCE: USERNAME\SPONSOR\PROJECT\JOBNAME (DATE,TIME)

Repeat Table 14.2.2.1 for the following:

Table 14.2.2.2: Analysis of Key Secondary Efficacy Endpoints (Per-Protocol Population)

Table 14.2.2.3: Sensitivity Analyses of Key Secondary Efficacy Endpoints (Intent-to-Treat Population) (Page 1 of 2)

Missing Values Imputed using Last Observation Carried Forward (LOCF) At Least 4-Point Reduction from Baseline in Weekly Average Worst Itch Numeric Rating Scale (WI-NRS) at Week 4	Placebo (N=xxx)	Serlopitant 5 mg (N=xxx)	P-value
Success	xx ( xx.x%)	xx ( xx.x%)	X.XXX a
Failure	xx ( xx.x%)	xx ( xx.x%)	
At Least 4-Point Reduction from Baseline in Weekly Average Worst Itch Numeric Rating Scale (WI-NRS) at Week 2 Success	xx ( xx.x%)	xx ( xx.x%)	x.xxx a
Failure	xx ( xx.x%)	xx ( xx.x%)	

P-value from a Cochran Mantel Haenszel (CMH) test stratified by Baseline WI-NRS used for randomization stratification.
 P-value from a repeated measures logistic regression with factors of treatment group, randomization stratification, visit and treatment group by visit interaction.

Table 14.2.2.3: Sensitivity Analyses of Key Secondary Efficacy Endpoints (Intent-to-Treat Population) (Page 2 of 2)

Repeated Measures Analysis on Observed Data At Least 4-Point Reduction from Baseline in Weekly Average Worst Itch Numeric Rating Scale (WI-NRS) at Week 4	Placebo (N=xxx)	Serlopitant 5 mg (N=xxx)	P-value
Success Failure	xx.xx% xx.xx%	xx.xx% xx.xx%	$x.xxx^b$
At Least 4-Point Reduction from Baseline in Weekly Average Worst Itch Numeric Rating Scale (WI-NRS) at Week 2 Success Failure	xx.xx% xx.xx%	xx.xx% xx.xx%	x.xxx b

P-value from a Cochran Mantel Haenszel (CMH) test stratified by Baseline WI-NRS used for randomization stratification.
 P-value from a repeated measures logistic regression with factors of treatment group, randomization stratification, visit and treatment group by visit interaction.

Table 14.2.3.1: Analysis of Additional Secondary Efficacy Endpoints (Intent-to-Treat Population)
(Page 1 of 6)

	Placebo (N=xxx)	Serlopitant 5 mg (N=xxx)	Normality P-Value	Treatment P-Value
Weekly Average Worst Itch Numeric Rating				

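### The repeated-measures sensitivity model is specified two ways: the text of SAP 6.8.2 omits the treatment-by-visit interaction that its table footnotes include

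*SAP*

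**What the plan says.** SAP 6.8.2 introduces the analysis so: "The second set of sensitivity analyses will be performed on observed data". It continues: "The dichotomized primary and key secondary WI-NRS endpoints will each be analyzed with a repeated measures logistic regression model". The factors are "treatment, stratification factor and visit (Weeks 1-10) as independent factors". No interaction is named, and neither is a working correlation.

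Protocol 8.9.2 lists the same terms with a shorter visit set: "treatment, stratification factor and visit (Weeks 2, 4, 10) as independent factors". It also plans a repeated-measures ANCOVA of change from baseline in DLQI to Week 10. SAP 6.8.2 contains no such analysis, and the shells in SAP section 10 have no table for it.

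The shells present the GEE results week by week. Table 14.2.1.3 has a repeated-measures row with its own p-value cell for Week 10. Page 2 of Table 14.2.2.3 has one row and cell for Week 4, labelled "Repeated Measures Analysis on Observed Data At Least 4-Point Reduction from Baseline in Weekly Average Worst Itch Numeric Rating Scale (WI-NRS) at Week 4", and another for Week 2. Footnote b, attached to these cells in both tables, reads: "P-value from a repeated measures logistic regression with factors of treatment group, randomization stratification, visit and treatment group by visit interaction".

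SAP section 8 states: "No changes to planned analyses".

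**The concern.** The primary and key secondary endpoints are a single variable, the WI-NRS 4-point response, read at Weeks 10, 4 and 2. A logistic model with treatment, stratum and visit as main effects assumes one treatment odds ratio for all visits, so it yields one treatment test. The shells ask for three tests. Footnote b supplies a model that can give three, but the section that defines the analysis does not.

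If the text is programmed, the same p-value appears under three week-specific labels. A reader would take the Week 2 and Week 4 cells as support for an early effect, when the number may be driven by later visits. The reverse can also happen: an effect that fades could make the Week 10 cell look supportive. In both cases the sensitivity analysis would no longer check the week-specific result it is meant to check.

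**Working it through.** **1. The specifications side by side**

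| Source | Terms | Visits |
|---|---|---|
| Protocol 8.9.2 | treatment, stratum, visit | 2, 4, 10 |
| SAP 6.8.2 | treatment, stratum, visit | 1 to 10 |
| Footnote b, Tables 14.2.1.3 and 14.2.2.3 | treatment, stratum, visit, treatment-by-visit | not stated |

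The plan gives no figure for this analysis that could be reproduced. Its power statement concerns an unstratified chi-squared test and does not enter here.

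**2. What each model tests**

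Let T be treatment (0 or 1), S the stratum and w the visit.

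- Text model: logit P = b0 + bT·T + bS·S + bV[w]. The serlopitant-minus-placebo difference at visit w is (b0 + bT + bS·S + bV[w]) − (b0 + bS·S + bV[w]) = bT. Stratum and visit cancel, so the log odds ratio and its Wald test are the same at Weeks 2, 4 and 10.
- Footnote model: add g[w]·T. The difference at visit w becomes bT + g[w], so each week has its own contrast and test.

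The SAP's statement that each endpoint will be analysed does not avoid this. Every endpoint is given the same responder variable and the same Weeks 1-10 visit factor, so three fits would be one fit repeated. The algebra is unchanged with the protocol's three visits.

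**3. One simulated dataset** (140 per arm, Weeks 1-10, an assumed growing effect, exchangeable working correlation, no missing data). The text model gives p = 0.0006 at Weeks 2, 4 and 10 alike. The footnote model gives p = 0.476, 0.166 and 0.023.

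**4. How often the two differ** (illustrative). The arm size of 140 and the two-sided 5% level come from SAP section 7. The weekly rates, the latent correlation of 0.6 and the absence of drop-out are assumptions. The Week 10 rates of 22% and 40% lie inside the Phase 2 ranges quoted there (20-25% and 33-47%). There were 300 trials per row, with visits 2, 4 and 10. Entries are the share of trials with p<0.05.

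| Assumed rates at Weeks 2 / 4 / 10 | Common test | Week 2 | Week 4 | Week 10 |
|---|---|---|---|---|
| Placebo 8 / 12 / 22%, serlopitant 8 / 12 / 40% | 62% | 4% | 5% | 87% |
| Placebo 8 / 12 / 22%, serlopitant 18 / 24 / 22% | 48% | 68% | 75% | 6% |

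The Monte Carlo standard error at 62% is √(0.62 × 0.38 / 300) = 0.028.

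A wider set of runs (3000 trials per setting) varied latent correlation, visit set, working correlation and drop-out (0%, or 15% by Week 10). Placebo rose linearly from 6% to 22%. With no effect through Week 2 and then a rise to 40% on serlopitant at Week 10, the common test gave p<0.05 in 47-91% of trials, against 3.5-4.8% for the Week 2 contrast. With a constant odds ratio the common estimate was unbiased, but the common test still reached p<0.05 in 93-100% of trials, against 59-62% for the Week 2 contrast, because it pools all visits.

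**5. Departures from the protocol.** The visit set differs and the DLQI repeated-measures ANCOVA is gone. If footnote b governs, the interaction is a third departure. SAP section 8 records none of them.

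**The case against.** The best reply is that the SAP already contains the right model. The shells belong to the same document, footnote b names the interaction in both tables, and a p-value in a row labelled by week, under that footnote, has one natural reading. The harm requires a programmer to disregard the footnote of the table being filled. This reply carries real weight and is why the point is small. It does not remove the contradiction: the SAP section that defines the analysis, and the protocol, both state another model, and nothing says which prevails. An interaction model also offers a treatment test averaged over visits as well as the weekly contrasts, so stating which is printed is a useful clarification, though its absence is not itself an error.

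A second reply is that the percentages follow from assumed weekly paths. That is correct. The documents give no weekly rates, within-subject correlations or drop-out rate. The single-test result rests on algebra alone and needs none of them.

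Third, naming no working correlation is not a fault in itself. With the interaction in the model and rates rising linearly (6% to 22% on placebo, 8% to 40% on serlopitant), the Week 10 contrast reached p<0.05 in 90-91% of trials with complete data and 85-87% with 15% drop-out completely at random, for either visit set and either working correlation. With drop-out of about 15% depending on the previous week's latent score it was 87-90%. The choice only needs to be made in advance.

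A reader might infer that the trial's significance claims are exposed. The documents do not support that. The primary and key secondary tests are CMH tests (SAP 6.7.1 and 6.7.2), the hierarchy in 6.1.8 applies to those endpoints, and 6.8.2 is a sensitivity analysis to which no alpha is assigned.

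**Conclusion.** The inconsistency is real and minor. SAP 6.8.2 and protocol 8.9.2 state a main-effects model, while footnote b of Tables 14.2.1.3 and 14.2.2.3 states an interaction model. Under the former, the three week-labelled cells would carry one test that is not week-specific. Separately, SAP section 8 is inaccurate about the visit set and the DLQI analysis.

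The effect is confined to a supportive analysis. The primary CMH test, alpha, power and testing hierarchy are unaffected. How misleading the cells would be depends on how the effect develops over time, which is unknown. With a constant odds ratio there is no bias, only mislabelled cells. The simulated percentages illustrate the mechanism and are not forecasts for this trial.

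Two stronger readings should be resisted. One is that the SAP plans the wrong model outright; its own footnotes say otherwise. The other is that the Week 10 result would be distorted in a known direction; that depends on the time course, the visit set and the working correlation, so no general statement is possible.

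**What to change.** - In SAP 6.8.2, and in protocol 8.9.2 if it is amended, add the treatment-by-visit interaction, with visit as a categorical factor, to match footnote b.
- In 6.8.2 and in footnote b of both tables, state that each p-value is the treatment contrast at the week named in the row.
- Use one visit set in both documents and name the working correlation in advance. Any reasonable choice will do.
- Either restore the DLQI repeated-measures ANCOVA to the SAP or record its removal in section 8, together with every other remaining departure from protocol 8.9.2.

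The cost is a sentence or two in 6.8.2, a few words in two footnotes and a short entry in section 8 or an edit to the protocol. No new data are needed. Restoring the DLQI analysis would add one model and a place for it in the shells.
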